#### **4.4. Early Withdrawal of Subjects**

##### **4.4.1. When and How to Withdraw Subjects**

Subjects have the right to withdraw fully or partially from the study at any time and for any reason without prejudice to his or her future medical care by the physician or at the institution.

Withdrawal of full consent for a study means that the subject does not wish to receive further investigational treatment and does not wish to or is unable to continue further study participation. This may include any follow-up in person, by phone, through third parties including relatives or friends, via discussion with other treating physicians, and by use of medical records. Subject data up to withdrawal of full consent will be included in the analysis of the study. Any subject may withdraw full consent to participate in the study at any time during the study. The Investigator will discuss with the subject appropriate procedures for withdrawal from the study.

##### **4.4.2. Data Collection and Follow-up for Withdrawn Subjects**

If a subject withdraws consent to participate in the study, attempts will be made to obtain permission and capture final photographic images of the keloids and measurement before being disenrolled.

If subjects are withdrawn prematurely from the study, Principal Investigator will consult with Study Statistician about handling any incomplete data set as compared to the full data set that fully supports the analysis. The Principal Investigator will determine whether to replace the withdrawn subject to achieve the goal of 5 completers.

Lost to follow up (LTFU) will be defined as a subject not answering or responding to 2 or more consecutive phone follow up calls after starting study medication, or after returned-receipt of 1 certified letter concerning discontinuation of participation in the study.

## 5. Study Drug

### 5.1. *Description*

#### 5.1.1. Rapamycin powder (from a supplier to Doyle's pharmacy)

Synonym: 23,27-Epoxy-3H-pyrido[2,1-c][1,4]oxaazacycloheptenatriacontine, AY 22989, Sirolimus;  
PubChem Substance ID [57654583](#)  
CAS No. 53123-88-9

An FDA-approved macrocyclic triene antibiotic forms a complex with FKBP12 that binds to and inhibits the molecular target of rapamycin (mTOR). Rapamycin (RAPA) is a potent immunosuppressant and has anticancer activity.

#### Mechanism of Action

The RAPA oral formulation developed by Pfizer (RAPAMUNE, sirolimus) inhibits T lymphocyte activation and proliferation that occurs in response to antigenic and cytokine (Interleukin [IL]-2, IL-4, and IL-15) stimulation by a mechanism that is distinct from that of other immuno-suppressants. Sirolimus also inhibits antibody production. In cells, sirolimus binds to the immunophilin, FK Binding Protein-12 (FKBP-12), to generate an immunosuppressive complex. The sirolimus: FKBP-12 complex has no effect on calcineurin activity. This complex binds to and inhibits the activation of the mammalian Target Of Rapamycin (mTOR), a key regulatory kinase. This inhibition suppresses cytokine-driven T-cell proliferation, inhibiting the progression from the G1 to the S phase of the cell cycle. Dosage forms and strengths include: oral solution (60mg/60mL in amber glass bottle) and oral tablets (0.5, 1, and 2mg).

Drug interactions with systemic use include: Inducers of CYP3A4 and P-gp may decrease sirolimus concentrations whereas inhibitors of CYP3A4 and P-gp may increase sirolimus concentrations. Avoid concomitant use of sirolimus with strong inducers (e.g., rifampin, rifabutin) and strong inhibitors (e.g., ketoconazole, voriconazole, itraconazole, erythromycin, telithromycin, clarithromycin) of CYP3A4 and P-gp. Avoiding consumption of grapefruit juice is also cited.

#### Safety

From oral administration, serious allergic reactions identified by the manufacturer include:

- swelling of face, eyes, or mouth
- trouble breathing or wheezing
- throat tightness
- chest pain or tightness
- feeling dizzy or faint
- rash or peeling of skin

In previous human studies cited earlier in this protocol, topical administration did not produce systemic or serious reactions. See Section 3.4 for Potential Risks due to topical RAPA. Participants will be instructed to notify the research team and get help right away if any of the above symptoms of an allergic reaction occur.

#### Storage

The powder is packaged 1 mg in a glass bottle with instructions to keep container tightly closed in a dry and well-ventilated place.

### **5.1.2. Petrolatum (Vaseline, vehicle only)**

#### Mechanism of Action

Petrolatum is a pale yellow to yellow-colored, translucent, soft unctuous mass. It is odorless, tasteless, and not more than slightly fluorescent by daylight, even when melted. Petrolatum is an inert material with few incompatibilities.

#### Safety

Petrolatum is mainly used in topical pharmaceutical formulations and is generally considered to be a nonirritant and nontoxic material. Animal studies, in mice, have shown petrolatum to be nontoxic and noncarcinogenic. Although petrolatum is generally nonirritant in humans following topical application, rare instances of allergic hypersensitivity reactions have been reported, as have cases of acne, in susceptible individuals following repeated use on facial skin. However, given the widespread use of petrolatum in topical products, there are few reports of irritant reactions. The allergic components of petrolatum appear to be polycyclic aromatic hydrocarbons present as impurities. The quantities of these materials found in petrolatum vary depending upon the source and degree of refining. Hypersensitivity appears to occur less with white petrolatum and it is often the preferred material for use in cosmetics and pharmaceuticals.

#### Storage

Petrolatum is an inherently stable material owing to the unreactive nature of its hydrocarbon components; most stability problems occur because of the presence of small quantities of impurities. On exposure to light, these impurities may be oxidized to discolor the petrolatum and produce an undesirable odor. Petrolatum should not be heated for extended periods above the temperature necessary to achieve complete fluidity (approximately 70°C/158°F). When heated to decomposition it emits acrid smoke and irritating fumes.

Petrolatum may be sterilized by dry heat. Petrolatum should be stored in a well-closed container, protected from light, in a cool, dry place.

#### Regulatory Status

GRAS listed. Accepted for use in certain food applications in many countries worldwide. Included in the FDA Inactive Ingredients Database (ophthalmic preparations; oral capsules and tablets; otic, topical, and transdermal preparations).

### **5.1.3. Compounded investigational product**

The investigational product and the placebo will be compounded and supplied by Doyle's Pharmacy in Houston, TX. A certificate of analysis from the source for the powder form of RAPA used in compounding can be provided. The literature states the compounded product will remain stable for 3 months (6) and extended stability testing will not be performed since new product can be ordered every 2 months through duration of the trial.

## **5.2. Treatment Regimen**

Each ointment (8% RAPA and placebo) will be applied to the appropriately designated keloid (RAPA experimental or placebo control) once daily for 6 months.

To avoid treatment confusion, the chosen keloids will be marked with a color-code by permanent marker; one color will be red, and a second will be green. Metered dispensers will be similarly color coded. The dispenser coded in red will be applied to the keloid labeled "right" and the lime green coded dispenser will be applied to the keloid labeled "left." Participants will be given color-coded photographs of the 2

keloids with identified landmarks to show which keloid receives which color-coded ointment.

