## 2. Study Objective

We will test the primary hypothesis that treatment of extant keloids with 8% topical RAPA ointment will regress keloid surface area and height.

Finally, to assess safety, we will gather data on anticipated common side effects of the medication, including any adverse drug reactions other than those listed as potential risks in Section 1.5 above.

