### **3.2. General Design**

Our pilot trial will use daily 0.5-1.0ml applications of 8% RAPA in a petrolatum vehicle to treat established keloid lesions in 5 persons with at least 2 chronic keloids in similar body regions (greater than 1-year duration). Treatment will be applied once daily for 6 months. One keloid will receive 8% RAPA ointment and the other keloid will receive petrolatum-only ointment as a control. Surface areas and height of keloids will be monitored pre- and post-treatment to evaluate responses.

We will measure keloid surface area and height changes pre-treatment and thereafter on a monthly basis using standardized digital photography with a tripod-mounted 8MP Canon S5is camera and calipers to measure keloid height (37).

Surface areas of all photographed lesions will be measured with Image J (<http://rsbweb.nih.gov/ij/index.html>), a public image-processing program that we used to analyze our preliminary data and will use the same approach in this study.

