## 4. Subject Selection and Withdrawal

#### 4.1. Inclusion Criteria

- Both sexes of ages 18-75 years in good general health
- All ethnic groups regardless of Veteran status
- Must have at least two (2) keloids present for at least 1 year, located in a similar body area that can be easily reached, and be willing to self-administer investigational ointment and placebo control
- Cognitive functioning (CLOX1  $\geq$ 10 and CLOX2  $\geq$ 12 ) sufficient to provide informed consent and be able physically to apply QD ointment to affected area
- Negative pregnancy test

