### **5.7.2. Dispensing of Study Drug**

Designated study staff maintain the drug purchase documentation and administration logs to track how, when and to whom the investigational drug was assigned. Inventory is managed by the research pharmacy. Study clinical staff keep administration records regarding dosing compliance, returned/unused drug, and any damaged or wasted study drug product. Routine Study Drug reconciliation will be performed based on clinical site policy and standard operating procedures.

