#### **6.1.2. Screening and Baseline**

Following consent and signature, participants will undergo minimal cognitive screen ( $\text{CLOX1} \geq 10$  and  $\text{CLOX2} \geq 12$ ) to ensure consent is valid. Study staff will:

- Obtain vital signs, height and weight, lab work (fasting) to ensure safety and rule out systemic infection (complete blood count [CBC], comprehensive metabolic panel [CMP], lipid panel, and urine pregnancy test)
- Document medical history, concomitant medication review, physical examination, and
- Perform evaluation of eligibility criteria listed in Sections 4.1 – 4.2 above.

Additional baseline activities and data collection to include:

- Current and recent medications within past 3 months
- Marking of keloid lesions selected for study
- Photography and caliper measurements
  - Standard calipers will be used for measuring height of keloid above normal skin surface
  - Photography and use of Image J software – Study staff will upload digitized photographs and transfer directly from camera to computer software; images of the keloid are visualized, and outlined with an electronic drawing tool contained in the software. The software calculates the surface area within the outlined region and stores the data in Image J for analysis (see Analysis section next page).
- 1st medication administration for education
- Investigational medication prescribed/dispensed for 1 month, and participant is given written instructions for self-administering medication and care of the study lesion

- Schedule Visit 2

Study staff will contact participants weekly by phone for follow up (3 calls) during the first month of treatment. If the participant has a SmartPhone, a scheduled video visit (such as FaceTime, IMO or Skype) is optional to conduct weekly interim assessments but not required. Visits 2-7 must be performed in the research area and cannot be conducted virtually due to photography standardization.

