## 7. Statistical Plan

### 7.1. Statistical Methods

For all analyses, the statistical threshold for significance will be set at  $p<0.05$ .

Keloid surface area and height data will be analyzed using ANOVA for repeated measurements using a

model similar to that described for the analysis of the preliminary data (see INNOVATION, above) with the addition of a random effect for subject (47). This analysis can be modified to include between-subject factors if such factors (sex, race, etc.) are identified for investigation.

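### The protocol does not require that chance, concealed from staff, decides which of a participant's two keloids gets rapamycin, so its only controlled efficacy contrast is open to confounding

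*Combined protocol and SAP*

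**What the plan says.** Section 3.2 states the design as "One keloid will receive 8% RAPA ointment and the other keloid will receive petrolatum-only ointment as a control". Section 5.2 adds that each ointment "will be applied to the appropriately designated keloid (RAPA experimental or placebo control"), so a designation step is assumed. The same section matches colours to lesions: "The dispenser coded in red will be applied to the keloid labeled 'right' and the lime green coded dispenser will be applied" to the left one. It does not say which colour contains rapamycin or whether that varies between participants.

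The lesions are chosen at Visit 1. Section 6.1.2 lists "Marking of keloid lesions selected for study" and gives no selection rule. Section 4.1 asks for at least two "keloids present for at least 1 year, located in a similar body area that can be easily reached"; it does not ask for similar size, height or activity.

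Section 2 reads: "We will test the primary hypothesis that treatment of extant keloids with 8% topical RAPA ointment will regress keloid surface area and height". The first objective in that section compares the rapamycin keloid with the control keloid; the second and third ask about regression of area and height after six months. Section 3.3 makes the primary outcome change in area and height. On significance, Section 7.1 begins "For all analyses, the statistical threshold for significance will be set at" and gives 0.05. Section 5.7.2 has staff keep "administration logs to track how, when and to whom the investigational drug was assigned".

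**The concern.** Using each person as his or her own control removes differences between people. It does not remove differences between two lesions on the same person. Only the allocation rule can do that, and none is stated. Two routes to confounding are left open.

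- **Choice of the treated lesion (main route).** If someone who can see both keloids decides which gets the drug, the choice may follow size, height, activity or apparent chance of response. Any of these may be related to how the lesion would change over six months regardless of treatment.
- **A common code (secondary route).** If rapamycin has the same colour in every participant, it is also always on the same labelled side. Drug and label are then completely aliased, and decoding one participant decodes all of them.

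The rapamycin-versus-vehicle contrast is the only controlled efficacy comparison in the trial. Five pairs are too few to detect or adjust for allocation bias afterwards, and Section 7.1 names no term for side, colour or baseline lesion difference.

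**Working it through.** **1. Does any section supply the allocation rule?** The candidates are:

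- Sections 3.2, 5.2 and 6.1.2 state that there are two arms, that a keloid is designated and that lesions are marked. None gives a method, an allocator or a time.
- Sections 1.4, 5.3 and 5.6 cover matched consistency and smell, participant blinding by colour, and opaque dispensers. The photography and caliper text after Section 6.1.2 adds three blinded photograph readers. All of these limit what people know after allocation; none decides which lesion gets the drug.
- Section 5.7.2 records assignment. A log neither generates nor conceals it.
- Section 7.1 has a random effect for subject, which is a model term. Elsewhere, randomisation is mentioned only for cited studies (Section 1.5 and the reference list).

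So no rule is found in the available text.

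**2. Which lesion differences survive the planned outcome?** Let lesion j have baseline B_j and natural change N_j, and let the drug effect be δ. The difference in change between the arms is δ + (N_rapamycin − N_vehicle). The B_j cancel, so a plain difference in starting size does not bias the contrast. A difference in expected N does, for example through regression to the mean, or if change depends on size or activity. Random allocation makes the expected value of (N_rapamycin − N_vehicle) zero; choice need not.

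**3. Illustration of size.** The plan gives no SD, effect size or power figure, so there is nothing to reproduce, and the inputs here are assumed. Take n = 5 completers (Section 3.1), α = 0.05 (Section 7.1, taken as two-sided) and a month-6 paired t-test in place of the planned ANOVA. Let d be the mean lesion difference in change, in SDs of the paired difference, with no drug effect.

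If the difference always favours the same arm, t is noncentral with 4 degrees of freedom and noncentrality d√5, and the critical value is 2.776. If the direction is randomised within each person, it takes a random sign in each pair (2,000,000 simulations per value of d).

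| d | d√5 | Same direction | Randomised |
|---|---|---|---|
| 0.25 | 0.559 | 0.072 | 0.050 |
| 0.5 | 1.118 | 0.141 | 0.051 |
| 1.0 | 2.236 | 0.401 | 0.056 |

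Five fair allocations have 2⁵ = 32 equally likely outcomes. At d = 1.0, the randomised rate breaks down by split as follows:

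| Split | Probability | Rejection rate |
|---|---|---|
| 5-0 | 2/32 = 0.0625 | 0.402 |
| 4-1 | 10/32 = 0.3125 | 0.074 |
| 3-2 | 20/32 = 0.625 | 0.013 |

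Weighted total: 0.0625 × 0.402 + 0.3125 × 0.074 + 0.625 × 0.013 = 0.056.

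**4. Link to the planned ANOVA.** Section 7.1 does not state the error term. If treatment is tested against subject-by-treatment, F(1,4) is the square of the paired t on the visit-averaged difference (critical F 7.709, the square of the unrounded 2.776). The rates then carry over with d in SDs of that difference. With another error term they would not.

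**The case against.** The strongest reply is that this is a five-completer pilot with stated safety and feasibility aims, and that silence about allocation is not evidence of biased allocation. Random allocation may be intended and simply unwritten. Attachment C in Section 15, an SOP for drug management, is listed as pending, and a few pages of the document were not available, so neither could be checked. This stands as a limit on the claim. It does not answer it, because a pending drug-handling SOP is no substitute for an allocation rule in the protocol.

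Several stronger readings are tempting and are not supported:

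- A reader might infer that staff will pick the lesion, or that red always holds rapamycin. The documents say neither; they only permit both.
- A reader might call this the only efficacy contrast. It is the only controlled one. The hypothesis in Section 2 names no comparator, and the second and third objectives can be read as before-after questions.
- A reader might infer that unequal baseline size by itself biases the result. Change from baseline, and flattening expressed relative to pre-treatment height, remove a simple difference in level.
- A reader might infer that one decoded case unmasks every outcome. The area readers are to be blinded to treatment and subject, so their unblinding is not shown. The exposure is mainly the caliper height measurement, for which no blinding is stated.

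**Conclusion.** The concern holds in this form: the available text does not require chance or concealed allocation between a participant's two keloids, and the only controlled efficacy contrast is therefore open to confounding. The main mechanism is a treated lesion chosen with knowledge of features that predict change. A common drug-to-colour code is a secondary possibility, for which the documents give no reason to expect a right-left difference.

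The conclusion rests on the text and does not depend on the error rates. The figures of about 7%, 14% and 40% follow from assumed differences of 0.25, 0.5 and 1.0 SD that always favour one arm, and from a paired t-test standing in for the ANOVA. They should not be read as this trial's false-positive rate. Confidence is high that the rule is absent from the text; no confidence attaches to any particular size of bias. Pilot status does not remove the point, because the plan states an efficacy hypothesis and tests it at 0.05, and masking after allocation cannot repair the comparison.

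**What to change.** State in Sections 3.2 and 5.2 that:

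- after both study keloids have been selected, labelled right and left, and measured at baseline, rapamycin is assigned to the red or the green dispenser for that participant from a pre-generated, concealed random list held by the pharmacy;
- the list is simple or balanced across participants, and the choice is stated;
- the assignment stays the same within a participant across all dispensings and reorders, and replacement participants (Section 4.4.2) take the next unused entry;
- the list is withheld from clinic staff and outcome assessors until analysis, except for a documented code break when needed for participant safety or event reporting;
- a named pharmacy applies the colour code, since Section 5.6 has the compounding pharmacy supply the dispensers and Section 5.7.2 has the research pharmacy manage inventory.

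The red-right and green-left matching can stay.

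**Cost.** One paragraph of text and a list to hold; no added visits or participants. The practical burden is labelling. Selection, baseline measurement and first application all fall at Visit 1, so participant-specific dispensers must be ready then, and the code must stay consistent when product is reordered, which Section 5.1.3 allows every 2 months.

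**Limits.** With simple randomisation of five participants, a 4-1 or 5-0 split occurs 12/32 = 37.5% of the time. After a 5-0 split, the illustrative error rate is as high as without randomisation. Balancing the list over colours gives a 3-2 split if there are no replacements, but it evens out labels only, not which lesion would have changed more. Five pairs remain non-confirmatory either way: an exact two-sided sign-flip test cannot go below 2/32 = 0.0625.

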### **5.3. Administration of Study Drug**

The initial application will be done in the laboratory for subject education. Color-coded permanent markers will be given to participants to re-mark sites as needed.

Participants will be responsible thereafter for applying the different ointments to the color designated keloids once daily for the study's duration. Two medication dispensers (8% RAPA and vehicle control) will be given to each subject on a monthly basis.

Subjects will be instructed to turn the Topi-CLICK of each container once per application and apply all the expressed ointment to the matching, color-coded keloid. Subjects will be instructed to apply ointments after bathing or showering, avoid washing the treated areas for at least 4 hours after application, avoid cross-contamination between sites by washing hands between applications, and use new disposable gloves (provided by study) for each ointment application.

By managing with color-coded dispensers to match lesions, the participants will be "blind" to which lesion is receiving placebo and which keloid gets active treatment.

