#### *Standardized digital photography and caliper measurements - Analysis*

We will measure keloid surface area and height changes pre-treatment and thereafter on a monthly basis using standardized digital photography with a tripod-mounted 8MP Canon S5is camera and calipers to measure keloid height (37). The key to successful use of photography is to maintain consistent image quality and thus ensure that images can be compared fairly. Factors that influence image quality will be standardized including lighting, 10cm distance from keloid surface, super macro camera setting, a proper center of focus perpendicular to the keloid surface, and inclusion of a standard millimeter ruler as a reference for calculation of surface areas by Image J. Photos thus taken will be suitable for sequential measurements over the 6 months of the study because they will be taken by the same camera at the same angle under identical conditions and using the same standardized ruler by the same person. Image J (<http://rsbweb.nih.gov/ij/index.html>), is a public domain image-processing program that can calculate area and pixel value statistics of user-defined selections, measure distances and angles, create density histograms, and line profile plots from digital images. Spatial calibration is available to provide real dimensional measurements in standard units such as mm^2. We used Image J to analyze our preliminary data and will use the same approach in this study. Surface areas of all photographed lesions will be measured with Image J by three trained reviewers blinded to all aspects of the photograph (date taken, treatment, subject, etc.). In addition, keloid height measurements (the maximum vertical elevation above normal skin) in millimeters will be made with calipers (37). Prior to measurements, we conduct training sessions for the readers to improve agreement among readers. Reviewers will be trained to standardized definitions (color, texture, etc.) of lesions thus minimizing inter-reviewer variability. We also will assess agreement within readers by repeating the measurements at a later time. The percentage of keloid flattening will be calculated as the percentage reduction normalized to pre-treatment height. Finally, we will record clinical observations of keloid changes to extend and subjectively verify our objective measurements.

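### No step keeps the red and green skin marks out of the photographs, so the stated reader blinding for keloid area is not secured

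*Combined protocol and SAP*

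**What the plan says.** **The marks.** Under section 5.2, "the chosen keloids will be marked with a color-code by permanent marker; one color will be red, and a second will be green". The dispensers carry the same colours, as one general rule: "The dispenser coded in red will be applied to the keloid labeled" right, and the lime green one goes to the keloid labelled left. Section 5.3 makes the marks last through follow-up: "Color-coded permanent markers will be given to participants to re-mark sites as needed".

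**The order of steps.** In the Visit 1 list in section 6.1.2, "Marking of keloid lesions selected for study" stands directly before photography and caliper measurement. Visits 2, 3 and 7 describe photography as the same as at baseline, and Visits 4 to 6 refer back to the visits before them.

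**The reading.** Area is traced by hand: "images of the keloid are visualized, and outlined with an electronic drawing tool contained in the software". The photography and caliper analysis section (6.1.3 in the table of contents) assigns this to "three trained reviewers blinded to all aspects of the photograph (date taken, treatment, subject, etc". The images are taken in super macro mode at 10 cm. The same section says "Reviewers will be trained to standardized definitions (color, texture, etc.) of lesions", so colour is part of what the readers look at.

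**What is not there.** The listed photographic controls cover lighting, distance, camera setting, focus, angle and ruler. None removes, crops or masks the ink. Section 15 lists the imaging instructions (Attachment D) as pending. No section says which colour or side holds rapamycin, whether that link differs between subjects, how it is set, or who holds the key.

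**The concern.** The plan promises readers who are blind to everything about the photograph, puts the ointment colour code on the photographed lesion, and gives no step to keep the two apart. A site that follows the listed steps could well hand the readers close-up images with the code in view.

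Keloid area is one of the two components of the primary outcome in section 3.3, and its value depends on where a person draws a line. A reader who can group images by ointment code may form an expectation about one code and trace it differently. If code and arm coincide, that difference goes into the comparison of rapamycin with vehicle, and more readings of the same kind do not average it out.

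The point concerns the photograph readers and the area measurement only. The stated blinding does not extend to the person who takes the caliper height, and that is a separate matter.

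**Working it through.** The plan gives no power calculation, effect size or variance that bears on this, so there is no figure to reproduce. The check is a reading of the sections together, with three small calculations that show what is exposed.

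**1. Can the code reach the reader?** Each lesion is marked in one of two colours (5.2). The marks are renewed as needed (5.3). Marking precedes photography in the Visit 1 list (6.1.2), and later visits follow the baseline procedure. The frame is a close-up (photography section). No step takes the ink out. Visible ink is the natural result of these steps, but no section states it.

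**2. What would be exposed?** Inputs: 5 completers (3.1), 2 keloids each (3.2), 7 visits with photographs (6.1 to 6.7), 3 readers.
- Images: 5 × 2 × 7 = 70.
- First readings: 70 × 3 = 210, before the repeat readings for within-reader agreement.

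**3. What does a visible colour reveal?** That depends on the colour-to-arm link, which the plan does not state. Two assumptions bracket it.
- *Same link for every subject:* colour sorts all 70 images into the two arms. A guess at which colour is rapamycin is right with probability 0.5, and one leak or one right guess unmasks all 5 pairs.
- *Link set independently at random for each subject:* guessing all 5 pairs correctly has probability 0.5^5 = 0.031. Colour then shows only which images carry the same code.

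The link also decides where a colour-related tracing error goes. Suppose red-marked lesions are traced larger than green ones by a fixed amount b, and red holds rapamycin in k of the 5 subjects. The error in the mean paired difference is b × (2k − 5)/5. With a constant link (k = 5 or 0) it is the whole of b, in one direction or the other. With k = 3 or 2 it is b × 1/5 in size.

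**4. How sensitive is area to the outline?** For a circle of diameter d traced 0.5 mm too far in, the proportional loss of area is 1 − ((d/2 − 0.5)/(d/2))².

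| Assumed diameter | Calculation | Area change |
|---|---|---|
| 10 mm | 1 − (4.5/5)² | 19% |
| 20 mm | 1 − (9.5/10)² | 9.75% |
| 30 mm | 1 − (14.5/15)² | 6.6% |

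The circular shape, the diameters, the 0.5 mm and its uniformity round the outline are all assumptions; the plan gives no lesion sizes. The table shows that small shifts in the line matter for small lesions. It does not predict a bias.

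**The case against.** The strongest reply is that colour is not treatment. Section 5.3 relies on the same colours to keep participants blind, so red and green are meant as a masked label. A reader who sees red learns nothing about the arm without the key. This stands. A reader of the plan might infer that the ink is an arm code and that the blinding has failed. The documents do not support that, because no section ties a colour to rapamycin.

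Four further replies have force.
- *Visibility is inferred.* No section says where the mark sits or that it falls in the frame. The pending Attachment D may deal with it. This stands as a limit on certainty. It does not supply the missing step.
- *Readers are also to be blind to date and subject.* It is tempting to say that they could watch one colour shrink. Colour alone does not put images in time order or match them within a subject, and nothing shows that those parts of the blinding fail.
- *The plan has other safeguards:* three readers, training, standard lesion definitions, repeat readings and a fixed camera set-up. These control variability and agreement. They do not remove an error that follows the colour code.
- *If the link varies by subject,* a colour-related error is spread over both arms. That is correct, as the formula above shows, but the plan does not say that the link varies.

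**Conclusion.** The concern holds in a limited form. The blinding of the area readers to treatment is stated, but the procedures described do not secure it: a colour code is put on the lesion and renewed, marking comes before photography, and nothing keeps the code out of the image.

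The documents do not show that the blinding is broken. That would need the ink to be in the frame, which is an inference, and the reader to know or guess the link, on which the plan is silent. How serious the gap is turns mainly on that link. If it is constant, a single disclosure or a guess with probability 0.5 unmasks all 5 pairs. If it is random by subject, the chance of guessing every pair is 0.031 and the remaining risk is much smaller. No bias in area can be estimated from the documents; the 19%, 9.75% and 6.6% show sensitivity under assumed lesion sizes and nothing more. The change is worth making because the endpoint is primary and hand-traced, and the cost is small.

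**What to change.** In section 6.1.2, the photography section and Attachment D, while the latter is still open:

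- Take the Visit 1 study photographs before the lesions are marked.
- At all visits, keep the marks outside the frame, or crop or digitally mask any remaining ink before the images go to the readers. If ink is to be cleaned off the skin instead, reconcile that step with the limits on skin applications to the keloid area in section 5.5.1.
- Give readers images under random file codes and in random order. Keep the colour-coded guide photographs made for participants (5.2) out of the reading set.

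In section 5.2, state that the link between colour or side and ointment is set at random for each subject, and name who holds the key. That person should not be a reader. The rule that pairs red with right and green with left can stay, because only the contents of the coded dispensers would vary.

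The cost is a wording change, a few minutes per visit, minor image handling, and an allocation list for the dispensers. It needs no extra visit or equipment.
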